4.2. Scientific Rationale for Study Design

This is a research study designed to explore feasibility and acceptability and initial efficacy of an EMA and text message intervention for stress management as a digital intervention.

4.2. Justification for Dose

N/A

4.3. End of Study Definition

The end of trial date is defined as the date at which all subjects have completed all activities shown in the Schedule of Assessments, all data has been entered, all data queries have been resolved, and the database has been locked.

5. Study Population

70 participants will be randomized to control (n=35) or intervention group (n=35)

5.1. Inclusion Criteria

Participants are eligible to be included in the study only if all of the following criteria apply:

1. Age 22 or older
2. Must reside in an Eastern Standard Time or Central Standard Time zone
3. Able to read and write in English as demonstrated by review and completion of an Informed Consent Form
4. Own an SMS enable smartphone (Android or iPhone OS4)
5. Scoring >5 on the 4-item Perceived Stress Scale (reflecting higher-than-average perceived stress; 15, 16)

5.2. Exclusion Criteria

Participants are excluded from the study if any of the following criteria apply:

1. Reported cognitive impairment and/or psychiatric disorders of the psychotic spectrum
2. Enrolled in another support study
3. Currently receiving psychotherapy through telehealth
4. PHQ-9 score of 20 or greater.

5.3. Lifestyle Considerations

N/A

5.4. Screen Failures

Individuals who do not meet the criteria for participation in this study (screen failure) may not be rescreened.

5.5. Recruitment

Between 70 and 120 participants will be recruited by advertisements posted on an internet job board, in order to randomize 70 participants.

[REDACTED]

[figure not shown]
[REDACTED]

6. Study Intervention and Concomitant Therapy

The study intervention is described below.

6.1. Study Intervention Administered

Text messages were developed by the principal investigator who is a trained clinical psychologist and cognitive behavioral therapist. The development of the text message library followed

6.2. Preparation/Handling/Storage/Accountability

Consent and welcome and intervention text messages will be delivered remotely using a web-based SMS messaging platform. To send and receive messages, a third-party web-based text messaging platform was used as the Internet gateway. Participants' cell phone numbers will be registered in the web-based text messaging platform at baseline. EMA and standard surveys will be collected through [REDACTED] a HIPPA approved secure survey platform that enables direct texting. The company is GDPR Compliant; data is stored securely and encrypted in transit, at rest, and on all backups to reduce the risk of data security breach. In addition, the company leverage [REDACTED] security features to further lock down access to data.

Text message send times and delivery status will be recorded. Participants will be informed that this is a one-way message program and not to reply, however record will be kept of any incoming messages from participants. A record of the number of times each participant attempts to contact the research team and the method of contact (i.e. via phone, email, text message) will also be kept.

Participants who text-back will be sent an automated text message as follows ‘From FACE stress: This is an automated reply. If this is an emergency and you are in need of immediate help call 911’. In addition, the content of the message will be reviewed by the research team who will determine an appropriate response including:

- No action required (e.g. text is related to content or acknowledgement)
- Action required on a study-related problem (e.g. participant reporting a technical problem or texting to withdraw from study)
- Action required on a different problem (e.g. text indicating high distress; response will be determined on a case-by-case basis and reviewed by the Principal Investigator and Medical Monitor)

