2.3. Benefit/Risk Assessment

Some participants may experience discomfort when completing assessments related to their stress levels and emotional well-being. Although participation in this study may reduce stress and improve emotional well-being, we recognize that individuals experiencing high stress may conversely face the risk of symptomatic worsening. Both text message platforms are two-way. This will allow for review of the evaluation of content and assessment to determine if participants are experiencing a worsening of stress and are in need of further support.

3. Objectives and Endpoints

Objectives	Outcomes

Primary
 
 • Feasibility of recruitment including eligibility rates and acceptance rates • Feasibility of delivering the intervention via text message • Acceptability of the intervention including dropout rates, percentage of completed assessments, adherence, and estimates of satisfaction 	
The main outcome of the FACE STRESS study is to evaluate feasibility and acceptability of an EMA and EMA plus text message intervention. Specifically, we will evaluate:
 
 • proportion of individuals who will contact us because interested to participate • the number of eligible individuals after the initial screening • time taken to recruit the sample • retention rates • the number and percentage of participants responding to any EMA text over the 3-week study • Satisfaction will be measured using both open-ended questions and likert-scaled questions to examine the acceptability and utility of the both EMA and intervention texts.

Secondary
 
 • Explore indicators of the EMA and text message intervention efficacy The effect sizes on reductions in perceived stress and other psychological symptoms will be estimated in the EMA and EMA+intervention groups at post-intervention, 1, 3 and 6-month time-points. 	
Secondary outcomes will measure:
 
 • Perceived stress and psychological overload • symptoms of anxiety and depression • symptoms of PTSD • positive and negative affects • resilience • psychological well-being

4. Study Design

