4.1. Overall Design

This study is a pilot randomized controlled trial with embedded qualitative research. Eligible participants who complete an informed consent form will be randomized to receive 3 weeks of EMA or 3 weeks of EMA plus the text message intervention for stress management based on a 1:1 allocation using random block sizes of 2.

Eligible participants will sign the consent form online before moving on to complete their baseline assessment. All participants will receive a copy of their signed consent form and will be provided with the research personnel's contact details. Participants who do not complete the baseline survey within 3 days from enrollment will be excluded from the study. Once their baseline is completed, participants will be randomized to receive:

- **Control:** 3 weeks of EMA, consisting of 2 text messages per day delivered at random times during waking hours to prompt participants to complete the survey
- **Intervention:**
 - o 1 week of EMA, consisting of 2 text messages per day delivered at random times during waking hours to prompt participants to complete the survey followed by
 - o 2 additional weeks of EMA in combination with 2 text messages per day with content related to stress management techniques.

At the end of the 3 weeks, participants in both groups will complete a post-intervention survey designed to evaluate participant satisfaction and to gather information for the purposes of improving the content of the text-message intervention. Changes in levels of psychological distress and well-being from baseline will be also evaluated.

At 1, 3 and 6-months post intervention, participants will be contacted via text message to complete a follow up survey. The follow up survey will include the same information collected at baseline with the exclusion of age, race, gender and adverse childhood events.

Participants from either group will be informed that they can withdraw from the study at any time without giving a reason by replying 'STOP' to any of the messages, or by contacting a member of the research team. No further information will be collected from participants who withdraw from the study.

Participants in the control group will be offered the opportunity to receive the intervention after the 6 months follow-up period. No data will be collected from this intervention.

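### Section 6.2 has participants told not to reply to messages, while section 4.1 has both groups told they can withdraw by replying STOP to any of them

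*Combined protocol and SAP*

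**What the plan says.** The combined protocol and SAP describes replying to study texts in three places.

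- **Section 6.2 (Preparation/Handling/Storage/Accountability)** sets the general instruction: "Participants will be informed that this is a one-way message program and not to reply". The same sentence then adds that a "record will be kept of any incoming messages from participants". The section goes on to describe an automated answer pointing to 911. It also describes staff review of what was sent, with action foreseen for texts asking to withdraw and for texts that suggest high distress.
- **Section 4.1 (Overall Design)** sets the withdrawal rule: "Participants from either group will be informed that they can withdraw from the study at any time without giving a reason by replying". The reply meant is the single word STOP. It may be sent in answer to every study text, and getting in touch with the team is offered as the alternative.
- **Section 2.3 (Benefit/Risk Assessment)**, after acknowledging that stressed participants may get worse, says: "Both text message platforms are two-way". It gives the purpose as follows: "This will allow for review of the evaluation of content and assessment to determine if participants are experiencing a worsening of stress".

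**The concern.** Sections 6.2 and 4.1 both specify information to be given to participants, and the two pieces of information cannot both be followed. Someone told not to reply has no reason to think that a STOP reply is expected or will be acted on. Someone told that STOP works on any message has been told that replying is allowed.

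Two things are at stake. The first is ease of withdrawal. Participation is voluntary, and a one-word reply is the least demanding way out that the protocol offers. The second is early notice of distress. The trial enrols people with higher-than-average perceived stress, and section 2.3 relies on two-way messaging as part of its answer to the risk of worsening. An instruction not to reply weakens that answer for anyone who takes it at face value.

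**Working it through.** No arithmetic applies. The check is to set the sentences side by side and ask whether any reading satisfies them together.

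**1. Section 6.2 against section 4.1.** Both sentences say what participants will be informed of, so neither is merely an internal note for staff. Section 6.2 gives a general instruction with no exception for STOP. Section 4.1 gives a permission that extends to every message, with no exception for any type of text. Nothing elsewhere in the document reconciles them. This is a direct contradiction.

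**2. Does limiting 6.2 to one platform help?** Section 6.2 describes two systems: a web-based SMS platform for the consent, welcome and intervention texts, and a separate survey platform for EMA and the standard surveys. Suppose the no-reply instruction covers only the SMS platform. The intervention arm still receives "2 additional weeks of EMA in combination with 2 text messages per day with content related to stress management techniques", and those texts go out through that platform. They fall within section 4.1's rule, which covers all messages. The conflict is narrower on this reading but remains. Section 2.3 also describes both platforms as two-way, not only the survey one.

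**3. Section 6.2 against section 2.3.** Section 2.3 states what the platforms can do and why that is useful. A platform that can receive texts can still be presented to participants as one-way, and part of the review in section 2.3 may be of returned assessments rather than free-text replies. So the two sections are in tension, not in strict contradiction. The tension still matters, because two-way messaging is offered in the benefit/risk section as a means of noticing worsening stress.

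**4. Section 6.2 against itself.** Logging, automatic answering and review of incoming texts can be a contingency for people who text despite the instruction. On its own this is consistent with discouraging replies. Read with section 4.1, however, a text asking to withdraw is something participants have been invited to send. Again this is tension, not contradiction.

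**5. What other routes remain?**

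- Withdrawal: contacting the research team, whose details every participant receives (4.1).
- Adverse events: collection at each contact point and an electronic reporting system (8.2).
- Silence: staff outreach once 2 consecutive days of EMA are missed (7.3).
- Oversight: Principal Investigator action on immediate safety concerns (8) and continuous Medical Monitor review (10.1.4.1).
- Texts sent anyway: still logged and reviewed (6.2).

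These routes limit the consequence. They do not make the two instructions agree.

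**The case against.** The best defence is that a general no-reply notice with an understood STOP exception is a common arrangement, and that section 6.2 points that way by listing withdrawal texts among those staff act on. The consent pages and the welcome text are not available for review and may already state the exception. This is plausible as to intent, and it means that what participants are actually told is unknown. It does not repair the protocol, because section 6.2 never mentions STOP and section 4.1 never mentions a no-reply rule.

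It is also fair to say that sections 2.3 and 6.2 supply only tension. That part of the defence stands, and the firm conflict is the one between 6.2 and 4.1.

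Three stronger readings are tempting, and the documents do not support them.

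- **Counting exposure.** A reader might multiply out the schedule: 2 × 21 = 42 EMA texts in each arm, plus 2 × 14 = 28 stress-management texts in the intervention arm, or 70 in all there. The reader might then say that each text carries conflicting instructions. No section says that any scheduled text carries either instruction. Participants may be informed once, at consent or welcome. The counts describe the schedule, not the size of the problem.
- **A distorted retention result.** Retention is a primary outcome, so a reader might infer that suppressed STOP replies inflate it. The documents give no reply rate or compliance rate from which to argue this. Under section 7.3, participants who fall silent and cannot be reached are treated as withdrawn in any case.
- **No way to report harm by text.** Section 8.2 refers to adverse events collected through the text platform, so a reader might infer that safety collection fails. The link is by implication only, and section 8.2 provides other means of collection.

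**Conclusion.** The point holds, and it is minor. Section 6.2's no-reply instruction directly contradicts section 4.1's STOP route, and it is in tension with section 2.3 and with section 6.2's own handling of incoming texts. A participant who follows 6.2 gives up the simplest way to withdraw and is discouraged from texting about distress.

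No numerical size can be attached, because the documents give no reply rate, adverse-event rate or compliance with the instruction. Randomisation, endpoints and analysis are unaffected. The conclusion rests on the protocol text alone. If the consent and welcome texts already state the STOP exception, the practical effect shrinks to an inconsistency between two sections that should still be corrected.

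**What to change.** Replace the no-reply instruction in section 6.2 with wording such as:

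> *You may reply STOP to any message to withdraw. This line is not monitored in real time and must not be used for emergencies (call 911); for problems or concerns, contact the research team using the details provided.*

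Keep the existing automatic answer, logging and review of incoming texts. Make the consent and welcome texts say the same if they do not already. Sections 2.3 and 4.1 can stay as they are.

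This wording deliberately stops short of advertising the line for safety concerns. Section 6.2 gives no monitoring hours or response time, so inviting distress texts could reassure people falsely. Opening that channel is a separate decision for the sponsor and is not needed to remove the contradiction. The statement about real-time monitoring assumes that none is in place, and should be adapted if it is.

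The cost is a wording amendment. It may need IRB/IEC approval (10.1.1), and if the consent form changes once enrolment has begun, current participants must be re-consented (10.1.2).

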6.3. Measures to Minimize Bias: Blinding

N/A

6.4. Study Intervention Compliance

Subjects will receive study intervention via text messages.

Subjects may remain in the trial, even if they are nonadherent with the digital intervention treatment.

A record of the digital intervention administered to each participant will be maintained. Intervention start and stop dates will also be recorded.

6.5. Dose Modification

N/A

6.6. Continued Access to Study Intervention after the End of the Study

Participants in the control group will be offered the opportunity to receive the intervention at the end of the study (after 6 months follow up). No data will be collected from this intervention.

6.7. Treatment of Overdose

N/A

6.8. Concomitant Therapy

N/A

7. Discontinuation of Study Intervention and Participant Discontinuation/Withdrawal

7.1. Discontinuation of Study

If the study intervention is permanently discontinued, any reported AEs/SAEs will be collected at the time of discontinuation.

7.2. Participant Discontinuation/Withdrawal from the Study

- A participant may withdraw from the study at any time at his/her own request or may be withdrawn at any time at the discretion of the investigator for safety, behavioral, or compliance reasons. This is expected to be uncommon.
- If a participant withdraws or is withdrawn from the Study, the sponsor will stop collecting new data from the participant, however, the sponsor may retain and continue to use any data collected before the participant withdraws or is withdrawn from the study.
- At the time of discontinuation from the study an early discontinuation visit will be conducted, as shown in the SoA. See SoA for data to be collected at the time of study discontinuation and follow-up and for any further evaluations that need to be completed.

7.3. Lost to Follow up

A participant will be considered lost to follow-up if he or she repeatedly fails to complete EMA and follow up surveys and is unable to be contacted by the study staff.

The following actions must be taken if a participant fails to complete 2 consecutive days of EMA survey:

- The study staff must attempt to contact the participant and address the missed survey and whether or not the participant wishes to and/or should continue in the study.
- Before a participant is deemed lost to follow up, the investigator or designee must make every effort to regain contact with the participant (where possible, 3 telephone calls and, if necessary, an email to the participant's last known email address). These contact attempts should be documented in the participant's study record.
- Should the participant continue to be unreachable, he/she will be considered to have withdrawn from the study.

8. Study Assessments and Procedures

[figure not shown]
- Study procedures and their timing are summarized in the SoA. Protocol waivers or exemptions are not allowed.
- Outcomes are self-reported by the subject through an electronic system. Study staff will review surveys and assessments for completeness.
- Immediate safety concerns will be addressed by the Principal Investigator immediately upon occurrence or awareness to determine if the participant should continue or discontinue study
- Adherence to the study design requirements, including those specified in the SoA, is essential and required for study conduct.
- All screening evaluations must be completed and reviewed to confirm that potential participants meet all eligibility criteria. The study coordinator will maintain a screening log to record details of all participants screened and to confirm eligibility or record reasons for screening failure, as applicable.

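### Section 7.3 can turn EMA silence plus failed contact into withdrawal from the whole study, losing later surveys from people who never asked to leave

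*Combined protocol and SAP*

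**What the plan says.** Section 7.3 opens with a general definition of loss to follow-up, which applies when "he or she repeatedly fails to complete EMA and follow up surveys and is unable to be contacted by the study staff". How often counts as repeated is not stated.

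The action list that follows has a much earlier start: "The following actions must be taken if a participant fails to complete 2 consecutive days of EMA survey". Staff must try to reach the participant, and the effort required before someone is deemed lost is "where possible, 3 telephone calls and, if necessary, an email". No minimum interval is given. The list closes with: "Should the participant continue to be unreachable, he/she will be considered to have withdrawn from the study". That is withdrawal from the study, not from EMA alone.

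Section 7.2 sets the consequence: "If a participant withdraws or is withdrawn from the Study, the sponsor will stop collecting new data from the participant". Nothing in the visible text keeps the Day 26 or the 1-, 3- and 6-month surveys open to someone withdrawn in this way. Section 8 rules out protocol waivers, so staff have little room to depart from the list.

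Section 6.4 leans the other way: "Subjects may remain in the trial, even if they are nonadherent with the digital intervention treatment".

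**The concern.** EMA runs on Days 5–25, before any follow-up survey is due. A list triggered by missed EMA can therefore reach its last bullet before the opening definition, which also mentions follow-up surveys, could be met. Someone who stops answering prompts and does not pick up the phone may still have been willing to answer a survey text weeks or months later. Under 7.3 and 7.2 that survey would not be sent.

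Two things are at stake.

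- **Secondary outcomes.** Section 3 asks for effect sizes at post-intervention and at 1, 3 and 6 months. The rule selects on non-response, so the outcomes it removes are those of low engagers. A participant withdrawn before Day 26 has no post-baseline survey and adds no outcome to the change-from-baseline model in Section 9.4. The visible text of that section describes no sensitivity analysis for missing surveys. The selection could differ by arm, because from the second week the intervention arm receives two further texts a day.
- **Feasibility criteria.** Section 9.1 judges success on survey completion (at least 33%) and on retention (at least 70%). If EMA silence can become study withdrawal, the first measure feeds the second. Retention has no stated time point, so how far this goes is open.

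**Working it through.** The plan gives no unreachable rate and no expected loss under 7.3, so it has no figure of its own to reproduce here. The inputs from the documents are 70 participants, 35 per arm (Section 9.2); two prompts a day for 21 days (Section 4.1); four post-baseline surveys, at Day 26 and 1, 3 and 6 months (Section 1.3); and the 70% retention criterion (Section 9.1). Everything else is marked as assumed.

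**1. Allowance under the retention criterion.** 0.70 × 70 = 49 retained, so 70 − 49 = 21 losses are allowed.

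**2. How easily the list is triggered.** Assume that prompts are answered independently with probability p, and that a day is missed when both prompts are missed: q = (1 − p)². Let a and b be the probabilities of no 2-day run so far, with the latest day answered or missed. Each day, a becomes (a + b)(1 − q) and b becomes (old a) × q. After 21 days, P(trigger) = 1 − (a + b).

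| Completion p | q | P(at least one 2-day silence) |
|---|---|---|
| 33% | 0.449 | 97% |
| 50% | 0.25 | 66% |
| 70% | 0.09 | 14% |
| 80% | 0.04 | 3% |

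A participant at the protocol's own 33% threshold would almost certainly trigger the list. If one missed prompt made a day count as missed, the figure at 70% completion would be 99%; the plan does not say which is meant.

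**3. From trigger to withdrawal.** Withdrawal also needs failed contact. Assume that 10–30% of triggered participants are unreachable (u). Expected withdrawals = 70 × P × u:

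- 33% completion: 6.8 to 20.3
- 50% completion: 4.6 to 13.9
- 70% completion: 1.0 to 2.9

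**4. Loss due to the rule itself.** Many unreachable people would not have answered later surveys in any case. Take 10–30% of all 70 as withdrawn, i.e. 7 to 21 people, which roughly matches the 33% row above. Assume that 20–40% of them would have answered a later survey.

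- Participants: 0.20 × 7 = 1.4 to 0.40 × 21 = 8.4
- Survey sets: 1.4 × 4 = 5.6 to 8.4 × 4 = 33.6, about 6 to 34
- Share of the 21-loss allowance: 1.4/21 = 7% to 8.4/21 = 40%

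At 70% EMA completion the same step gives 0.20 × 1.0 = 0.2 to 0.40 × 2.9 = 1.2 participants.

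**5. Precision.** The 95% half-width for a standardised difference is 1.96 × √(2/n per arm). It is 0.47 at n = 35, and 0.49, 0.52 and 0.56 after losing 10%, 20% and 30% (n = 31.5, 28, 24.5). Only part of that widening comes from the rule. In the worst case above, recovering 8.4 people gives n = 24.5 + 4.2 = 28.7 and a half-width of 1.96 × √(2/28.7) = 0.52 instead of 0.56.

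**The case against.** The best defence is that 7.3 can be read as a whole. Two missed days alone trigger only a contact attempt, and a participant who is reached and wishes to continue may stay. The second bullet refers to being deemed lost to follow-up, which points back to the wider opening definition, and it asks for every effort first. On that reading nobody is withdrawn after a few quiet days. This stands as a possible reading. It does not settle the matter, because the last bullet does not wait for a missed follow-up survey and sets no time.

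A reader might draw several stronger conclusions that the documents do not support.

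- **That 7.3 contradicts 6.4.** Section 6.4 is permissive and concerns nonadherence with the intervention, not EMA silence with failed contact. A nonadherent participant who can be reached may stay under both. This is a tension.
- **That Section 4.1 independently stops the data.** Its sentence on collecting nothing further comes straight after the participant's own STOP request. The stop for an administrative withdrawal rests on 7.2.
- **That the rule could use up the whole retention allowance.** If 30% of 70 were withdrawn, that would be 21 people, but most of them would be missing under any rule. Only the recoverable part belongs to the rule.
- **That retention is understated by rule.** Retention is not defined closely enough to say so. If it means survey response, only the recoverable few change it.

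It is also fair that the outcomes affected are secondary and exploratory in a 70-person pilot, and that neither the size of the bias nor any difference between arms can be computed from the documents.

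**Conclusion.** The point holds as a drafting fault with a real but limited consequence. Followed literally, the last bullet of 7.3 together with 7.2 ends survey collection for people who did not ask to leave, and it selects them on non-response. The opening sentence of 7.3 and Section 6.4 sit uneasily with this, and neither overrides it.

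The loss due to the rule is about 1–8 participants, or 7–40% of the 21 losses allowed. This rests on two assumed ranges, neither of which the documents can confirm. The upper end needs EMA completion near 33% and 30% of triggered participants unreachable; at 70% completion the loss is about one participant or fewer. The main harm is the selective loss of low engagers' outcomes. The change is worth making because it is cheap, not because the pilot fails without it.

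**What to change.** Reword the last bullet of 7.3. An unreachable EMA non-responder is recorded as an EMA non-responder and is still sent the scheduled Day 26 and 1-, 3- and 6-month survey texts, unless he or she actively withdraws by STOP or by request. Bring the opening sentence of 7.3 and Section 6.4 into line with this. State in Section 9.1 the time point at which retention is counted. Report active withdrawal, EMA non-response and survey non-response separately by arm.

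The cost is a protocol wording change, some unanswered texts, and a little staff or platform work; the documents do not say that survey texts are sent automatically. There is one knock-on effect. Section 8.3.3 ends SAE follow-up at, among other points, loss to follow-up as defined in 7.3, so the sponsor must reconcile the changed status with that section. The sponsor should also state whether intervention texts continue for such a participant, which the present wording leaves open once withdrawal no longer follows.

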1.3. Schedule of Assessments (SoA)

Procedure	Pre-Enrollment	Day 1	Days 2-4	Days 5-25	Day 26	1 Mo. Post-Study	3 Mos.	6 Mos.	E/D ¹
Telephone Contact	X								X
Inclusion and Exclusion Criteria	X								
Demography	X								
Informed Consent		X							
Baseline Assessment			X						
EMA+Intervention				X					
Post Intervention Assessment					X				
Follow Up Assessment						X	X	X	

Protocol DL-FACE-101 v1.0

Procedure	Pre-Enrollment	Day 1	Days 2-4	Days 5-25	Day 26	1 Mo. Post-Study	3 Mos.	6 Mos.	E/D ¹
AE/SAE Reporting		X	X	X	X	X	X	X	X
1. Early Discontinuation									

2. Introduction

Click Therapeutics digital therapeutic software applications are integrated with the unique feature of a personalized messaging system. Personalized messages provide the opportunity to tailor the intervention to the specific needs of the individual patient. This study will be pivotal in addressing the feasibility of adding to Click's platform a stand-alone text message intervention for stress management. Many patients with psychiatric and medical conditions suffer with chronic stress which exacerbate course and progression of the disease. A stand-alone text message intervention will represent an important feature to add to Click's platform across indications to target patients with high levels of stress.

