8.3.1. Time Period and Frequency for Collecting AE and SAE Information

[figure not shown]
All AEs and SAEs will be collected from the signing of the informed consent form (ICF) until the 6 months follow-up as specified in the SoA (Section 1.3).

All SAEs will be recorded and reported to the investigator immediately. Under no circumstance should this exceed 24 hours, as indicated in Appendix 3. The investigator will submit any updated SAE data to Designated Click Medical Monitor within 24 hours of it being available.

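### Section 2.3 relies on message and assessment review to detect worsening, but no visible text makes a worsening survey score a trigger for action

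*Combined protocol and SAP*

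**What the plan says.** - **Risk.** Section 2.3 recognises that "individuals experiencing high stress may conversely face the risk of symptomatic worsening".
- **Mitigation.** The same section calls both text platforms two-way and continues: "This will allow for review of the evaluation of content and assessment to determine if participants are experiencing a worsening of stress".
- **Messages.** Section 6.2 has the research team read incoming texts and sort them by the response needed. One category is "text indicating high distress; response will be determined on a case-by-case basis and reviewed by the Principal Investigator and Medical Monitor". The same section also states: "Participants will be informed that this is a one-way message program and not to reply".
- **Surveys.** Section 8 says: "Study staff will review surveys and assessments for completeness". Its next bullet is a general safety clause: "Immediate safety concerns will be addressed by the Principal Investigator immediately upon occurrence or awareness".
- **Adverse events.** Section 8.3.1 says: "All AEs and SAEs will be collected from the signing of the informed consent form (ICF) until the 6 months follow-up". The Schedule of Assessments (Section 1.3) accordingly marks "AE/SAE Reporting" at every time point from Day 1.
- **Entry limit.** Section 5.2 excludes anyone with a PHQ-9 score of 20 or more.
- **Outcomes.** Section 3 lists anxiety and depression symptoms as secondary outcomes. Section 4.1 says the follow-up survey repeats the baseline content apart from a few named items.

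**The concern.** Section 2.3 names two sources for detecting worsening: what participants write and what their assessments show. The first has a reader, a high-distress category and an escalation route, but participants are told not to use it. For the second, the visible text describes only a completeness check.

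The study enrolls people for raised stress and follows them remotely for six months after the intervention. The sponsor treats a PHQ-9 of 20 or more as unsuitable at entry, yet no visible text says what happens if someone reaches that level on study. A participant could return every survey, send no text, report no adverse event, and have a severe score stay unread until analysis.

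**Working it through.** The plan gives no figure to reproduce. The check is to ask, for each provision, what sets it in motion and whether a survey score can do so.

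| Provision | What sets it in motion | Can a survey score start it? |
|---|---|---|
| 6.2, message review | An incoming text | No |
| 7.3, staff contact | Two consecutive days without EMA surveys | No; the trigger is non-response |
| 8, immediate safety concerns | The Principal Investigator's awareness | Only if someone reads the score; no reader is named |
| 8.2, 8.3 and 8.3.2, adverse events | Collection at each contact point, participant report, detection by the investigator and designees, preferably by verbal questioning | No score is named |
| 7.2, withdrawal for safety | The investigator's judgment | Only once the investigator knows |
| 10.1.4.1, Medical Monitor | Continuous monitoring of safety data | Scores are not named as safety data; the standard surveys sit under Efficacy Assessments (8.1) |

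Two details limit how far the adverse-event route reaches.

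1. Verbal questioning needs a conversation. The Schedule of Assessments marks telephone contact only at pre-enrollment and early discontinuation, and Section 4.1 makes the follow-up contacts by text message. A participant who stays in and answers the EMA prompts has no scheduled call from consent to month 6.
2. Section 10.3.1 counts exacerbation of a pre-existing condition as an adverse event. It leaves out expected progression of the condition under study unless this is more severe than expected. Worsening stress is therefore not clearly an adverse event.

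**Workload of the proposed check.** Inputs: 70 participants (Section 5); four post-baseline standard surveys (Day 26 and months 1, 3 and 6); the retention threshold of 70% and the survey-completion threshold of 33% (Section 9.1).

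- Maximum surveys to read: 4 x 70 = 280.
- With retention at 70% throughout: 0.70 x 70 = 49 people, and 4 x 49 = 196 surveys.

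The documents give no rate of severe scores, so the flag rates below are assumptions.

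| Assumed share of surveys flagged | Of 280 | Of 196 |
|---|---|---|
| 2% | 5.6 | 3.9 |
| 5% | 14 | 9.8 |
| 10% | 28 | 19.6 |
| 20% | 56 | 39.2 |

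**What the check leaves out.** Its earliest possible flag is at Day 26. Days 5-25 are 21 days. Assuming two EMA prompts a day in both arms throughout, that is 21 x 2 = 42 prompts per person and 42 x 70 = 2,940 in all. At 33% completion, 0.33 x 2,940 = about 970 responses would stay outside the check.

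**The case against.** The strongest objection is visibility. Section 8.1 breaks off after the opening baseline item, so the instruments, the EMA items and any alert rule there are unseen. Text that cannot be seen cannot be called missing. This stands, and it is why the point is confined to the visible text and shrinks to a cross-reference if a rule exists.

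Section 2.3 can also be read two ways. If its review covers survey answers, the plan already states the intention and lacks only a reader and a trigger. If it covers incoming messages alone, Section 6.2 supplies the review. Either reading softens the inconsistency. Under the second, though, the mitigation rests on replies that participants are told not to send.

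A reader might infer that nobody looks for worsening, or that every safeguard waits for the participant to speak up. The documents do not support this. Section 8.3 makes the investigator and designees responsible for detecting events, Section 8.2 collects them at each contact point, Section 8.3.2 prefers verbal questioning, and the Medical Monitor's role includes signal detection. Nor does Section 8 say that completeness is the sole purpose of survey review. What survives is narrower: none of these provisions makes a score a trigger, and scheduled telephone contact is sparse.

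Finally, the check begins only after the intervention ends and leaves EMA responses alone. That is a real limit. It does not remove the value of reading scores over the six months that follow.

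**Conclusion.** The point holds as a modest safety improvement. In the visible text, a worsening survey score triggers nothing, and a compliant participant whose depression score reaches the Section 5.2 exclusion level could go unnoticed if the plan is followed as written. Confidence is medium because part of Section 8.1 is unseen.

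The size is a workload: at most 280 surveys to read, or 196 with retention at 70%. The number of flags depends wholly on an assumed rate. The conclusion also assumes that a depression score is collected after baseline. Sections 3 and 4.1 suggest so, but PHQ-9 is visible only as an entry criterion.

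A reader might go on to infer that participants are being harmed or that safety monitoring is absent. The documents give no rate of worsening, and the general provisions do provide some active detection, so neither inference is supported.

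**What to change.** Amend the Section 8 bullet so that staff review each post-baseline standard survey (Day 26, months 1, 3 and 6) for completeness and for a depression score at or above the Section 5.2 exclusion level. That is a PHQ-9 of 20 or more if the instrument is repeated, otherwise the severe cut-off of the instrument used. Send flags to the Principal Investigator and Medical Monitor by the Section 6.2 route, identically in both arms, and report flags by arm.

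A rise-from-baseline criterion is optional and for the sponsor to set. It would catch changes that a level misses, such as a PHQ-9 moving from 2 to 19.

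The flag does not cover EMA responses in Days 5-25. The EMA items are not visible, so no EMA threshold is proposed. If the unseen part of Section 8.1 already holds an alert rule, cross-reference it from Sections 2.3 and 8 instead.

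The cost is a few sentences and a score check within a review staff already make, with no new visit or instrument. The downside is some false flags and some extra staff contact in both arms, including the EMA-only control. This could slightly affect retention, which is a primary outcome, or the contrast between arms.
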